7.3.3 Safety analyses

Since the main objective of this study is long term safety, the primary focus would be on incidence of drug-related AE and serious infection.

Adverse events will be coded using the Medical Dictionary for Regulatory Activities (MedDRA) coding dictionary. Summary tables and listings will be produced. All adverse events with an onset between start of treatment and end of the residual effect period (REP), a period of 20 weeks after the last dose of trial medication, will be assigned to the treatment period for evaluation.

All treated patients will be included in the safety analysis.

Statistical analysis and reporting of adverse events will concentrate on treatment-emergent adverse events. To this end, all adverse events occurring between start of treatment and end of the residual effect period will be considered 'treatment-emergent'. Adverse events that start before first drug intake and deteriorate under treatment will also be considered as 'treatment-emergent'. Frequency, severity, and causal relationship of adverse events will be tabulated by system organ class and preferred term after coding according to the current version of the Medical Dictionary for Drug Regulatory Activities (MedDRA). Safety analyses will focus on adverse events related to early discontinuation, immune suppression and injection site effects.

Laboratory data will be analysed both quantitatively as well as qualitatively. The latter will be done via comparison of laboratory data to their reference ranges. Values outside the reference range as well as values defined as clinically relevant will be highlighted in the listings. Treatment groups will be compared descriptively with regard to distribution parameters as well as with regard to frequency and percentage of patients with abnormal values or clinically relevant abnormal values. Analysis of laboratory measures will focus on haemotologic measures of immune suppression.

Vital signs, physical examinations, or other safety-relevant data observed at screening, baseline, during the course of the trial and at the end-of-trial evaluation will be assessed with regard to possible changes compared to findings before start of treatment.

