10.2 Analysis of Adverse Events

10.2.1 Treatment-Emergent Adverse Events

Treatment emergent AEs (TEAEs) are defined as events that begin or worsen either on or after the first dose of the study drug in the current study and within 140 days after the last dose administration of the study drug in the current study for subjects not rolling over into Study M16-000 Sub-Study 3 or until the first dose of the study drug of Study M16-000 sub-Study 3 if the subject is enrolled into Study M16-000 Sub-Study 3.

Events where the onset date is the same as the study drug start date are assumed to be treatment-emergent, unless the study drug start time and the adverse event start time are collected and the adverse event start time is prior to the study drug start time. If an incomplete onset date was collected for an adverse event, the event will be assumed to be treatment-emergent unless there is other evidence that confirms that the event was not treatment-emergent (e.g., the event end date was prior to the study drug start date).

All analyses of AEs will be based on the number of patients with AEs (not the number of AEs).

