10.2.1.1 Adverse Event Overview

The number and percentage of subjects experiencing TEAEs will be summarized for the following AE categories.

Any treatment-emergent adverse event.

Any treatment-emergent adverse event that was assessed with a Reasonable Possibility of being related to study drug by the Investigator.

- Any treatment-emergent severe adverse event.
- Any treatment-emergent serious adverse event.
- Any treatment-emergent adverse event leading to discontinuation of study drug.
- Any treatment-emergent adverse event leading to death.
- Any treatment-emergent adverse event of safety interest.

Any event with an unknown severity will be considered severe and any AE with an unknown relationship will be considered drug related.

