10.2.1.2 Adverse Events by System Organ Class and Preferred Term

The number and percentage of subjects experiencing TEAEs will be tabulated using primary Medical Dictionary for Regulatory Activities (MedDRA) system organ classes (SOCs) and preferred terms (PTs) for each treatment group according to Version 18.0 or higher of the MedDRA coding dictionary. The SOCs will be presented in alphabetical order, and the PTs will be presented in alphabetical order within each SOC.

A subject who reports more than 1 AE in different SOCs will be counted only once in the overall total. A subject who reports 2 or more different PTs, which are in the same SOC, will be counted only once in the SOC total. Subjects reporting more than 1 AE for a given PT will be counted only once for that term (most severe incident for the severity tables and most related incident for the relationship tables).

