10.2.1.7 Adverse Events by 100 Patient Years

TEAEs will be summarized by event rate per 100 patient years, defined as

$$100 \times \frac{\text{Number of TEAEs}}{\text{Total Patient Years}}$$

where total patient years is defined as below.

- Total patient years of SC period is defined as (min (the last risankizumab SC dose date in Study M15-989 + 140 days, the first dose date of risankizumab in Study M16-000 sub-Study 3) - the first dose date of risankizumab SC in Study M15-989)/365.25.
- Total patient years of IV period is defined as (min (the last risankizumab IV dose date + 140 days, the first dose date of risankizumab SC) - the first dose date of risankizumab IV in Study M15-989)/365.25.
- Total patient years of "all risankizumab" is defined as (min (the last risankizumab dose date in Study M15-989 + 140 days, the first dose date of risankizumab in Study M16-000 sub-Study 3) - the first dose date of risankizumab in Study M15-989)/365.25.

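### SAP 10.2.1 bases every AE analysis on patients, yet its one exposure-adjusted analysis (10.2.1.7) counts events, and no patient-based AE summary allows for unequal follow-up

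*SAP*

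**What the plan says.** SAP 10.2.1 sets a general rule: "All analyses of AEs will be based on the number of patients with AEs (not the number of AEs". No exception is written.

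SAP 10.2.1.7, a subsection of 10.2.1, says: "TEAEs will be summarized by event rate per 100 patient years, defined as" 100 times a ratio whose numerator is "Number of TEAEs". The denominator is total patient-years, defined separately for the SC period, the IV period and all risankizumab. For all risankizumab it runs from first dose to "min (the last risankizumab dose date in Study M15-989 + 140 days, the first dose date of risankizumab in Study M16-000 sub-Study 3". It does not stop at a patient's first event. The section does not say whether the rate will be produced for drug-related events, SAEs or areas of safety interest (ASIs).

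The other AE tables count patients without exposure. SAP 10.2.1.1: "The number and percentage of subjects experiencing TEAEs will be summarized for the following AE categories". SAP 10.2.1.2: "Subjects reporting more than 1 AE for a given PT will be counted only once for that term". SAP 10.2.2 treats SAEs and discontinuations the same way.

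Protocol 7.3.3 says that "the primary focus would be on incidence of drug-related AE and serious infection".

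For patients who roll over, SAP 10.2.1 keeps events treatment-emergent "until the first dose of the study drug of Study M16-000 sub-Study 3 if the subject is enrolled" in that study, without repeating the 140-day limit that 10.2.1.7 puts on their patient-years.

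**The concern.** The general rule excludes the numerator that the subsection uses. The SAP is meant to guide programming, so the exception should be written rather than inferred.

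Settling the wording leaves a larger gap. Long-term safety is the primary objective and the protocol's focus is incidence, but no patient-based rate allows for time at risk. Follow-up is clearly unequal. The Amendment 4 rationale in protocol Section 11 says the study will be terminated and treatment durations will differ. SAP 8.2.1 tabulates exposure in bands from 1–84 days to over 924 days. In Flow Chart 3 the IV period runs from week 4 to the first SC dose at week 16, about 12 weeks, while SC dosing can run to week 216. Percentages from these periods will stand side by side as treatment groups (SAP 5.2).

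**Working it through.** The documents state no AE rate or event count, so there is no plan figure to reproduce.

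**Inputs from the documents.** N = 60 (SAP 4.2). Longest follow-up: SC doses span 200 weeks (SAP 6.4, Table 1), so 1400 + 140 = 1540 days, and T = 1540/365.25 = 4.22 years.

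**Assumptions.** Shorter T of 1.5 and 2.5 years, equal for all patients within a scenario; mean event rate L per PY; events either Poisson with the same rate for everyone, or Poisson with gamma frailty of shape 1 (rates vary between patients).

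**Three rates per 100 PY**

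- (a) Events over total PY, as in 10.2.1.7: 100 × L.
- (b) Patients over total PY, which is the 10.2.1 numerator placed in the 10.2.1.7 denominator: 100 × P/T, where P is the probability of at least one event.
- (c) Patients over PY to first event: 100 × P divided by mean time at risk.

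With frailty, P = LT/(1 + LT) and mean time at risk = ln(1 + LT)/L. With homogeneous Poisson, P = 1 − exp(−LT) and (c) equals 100 × L.

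**One case in full** (frailty, L = 2, T = 2.5). Total PY = 60 × 2.5 = 150; events = 2 × 150 = 300; patients = 60 × 5/6 = 50; time at risk = 60 × ln(6)/2 = 53.75 PY. So (a) = 300/150 = 200; (b) = 50/150 = 33; (c) = 50/53.75 = 93 per 100 PY.

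**All frailty cases**

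| L per PY | T (years) | (a) | (b) | (c) | (a)/(b) | (a)/(c) |
|---|---|---|---|---|---|---|
| 2 | 1.5 | 200 | 50 | 108 | 4.0 | 1.9 |
| 2 | 2.5 | 200 | 33 | 93 | 6.0 | 2.2 |
| 2 | 4.22 | 200 | 21 | 80 | 9.4 | 2.5 |
| 0.03 | 1.5 | 3.00 | 2.87 | 2.93 | 1.05 | 1.02 |
| 0.03 | 2.5 | 3.00 | 2.79 | 2.89 | 1.08 | 1.04 |
| 0.03 | 4.22 | 3.00 | 2.66 | 2.83 | 1.13 | 1.06 |

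Under homogeneous Poisson (a) equals (c), and (b) at L = 2 is 63, 40 and 24 for the three values of T. For L from 0.01 to 3 under both models, (a)/(b) runs from 1.01 to 13.7.

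**Crude percentages.** Assume the same constant first-event hazard h in a 12-week IV period (84/365.25 = 0.23 years) and a 3-year SC period. The percentage with an event is 1 − exp(−h × time).

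| h per year | 12 weeks | 3 years | ratio |
|---|---|---|---|
| 0.03 | 0.69% | 8.6% | 12.5 |
| 0.5 | 10.9% | 77.7% | 7.2 |
| 2 | 36.9% | 99.8% | 2.7 |

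The risk per unit time is identical in each row; a first-event rate would be the same in both periods.

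**The case against.** The strongest reply is that 10.2.1.7 is the specific rule. It has its own heading, calls itself an event rate and gives an explicit formula, so a programmer has one calculation to run. The 10.2.1 sentence then reads naturally as governing the count-and-percentage tables. Those tables are legitimate incidence proportions, and set beside the event rate they help show whether a few patients with repeated events drive it. Protocol 7.3.3 asks for incidence but does not require a first-event rate, and this is a descriptive single-group study of about 60 patients. All of that stands. It does not supply a patient-based rate that allows for unequal follow-up.

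Four stronger readings are tempting, but the documents do not support them.

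- A reader might infer that the reported rate is ambiguous by a large factor. Patients over total PY is written nowhere in the SAP. It arises only by combining the numerator of one section with the denominator of another, and for rare events, which may include serious infection, it lies close to the event rate.
- A reader might infer that the 10.2.1.7 rate is invalid. It is a valid event rate; it answers a different question from patient incidence.
- A reader might infer that only one overall rate is planned. Three are defined, for IV, SC and all risankizumab, though none is split by time on drug.
- A reader might infer that roll-over events are counted without limit. SAP 6.2 bars from analysis any data collected more than 140 days after last dose (although under the heading of final observation). Protocol 7.3.3 ends treatment-emergence at 20 weeks, and protocol 5.2.2.2 collects AEs through the same period. A mismatch needs a gap above 140 days between the last dose here and the first M16-000 dose, and nothing in the documents shows that this occurs.

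**Conclusion.** The wording conflict is certain, current and near-clerical by itself. The point of substance is that no patient-based AE summary is adjusted for exposure, although follow-up is unequal and incidence is the protocol's stated safety focus.

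The size depends on AE frequency, for which the documents give no figure. Under the frailty assumption, event-based and patient-based rates nearly agree at 3 per 100 PY: about 5–13% apart against patients over total PY, and 2–6% against a first-event rate. For frequent TEAEs at 200 per 100 PY, the event rate is about 4 to 9 times patients over total PY and 1.9 to 2.5 times the first-event rate. If all patients shared one constant rate, event and first-event rates would coincide. For rare events the 10.2.1.7 rate is therefore a fair stand-in, but only if it is produced for the categories of interest, which the SAP does not say. The crude IV and SC percentages are furthest apart for those same rare events. This is a worthwhile low-cost improvement and does not invalidate the planned safety analysis.

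**What to change.** 1. In SAP 10.2.1, limit the patient-count sentence to the count-and-percentage tables and state that 10.2.1.7 is the exception.
2. Add patients with a first event per 100 PY at risk, with time censored at first event, for drug-related TEAEs, SAEs, serious infections and the other ASIs, by IV, SC and all risankizumab. A further split by exposure interval is optional, because late counts will be sparse.
3. End the TEAE window for roll-over patients at the earlier of last dose + 140 days and first M16-000 dose. This agrees with SAP 10.2.1.7, SAP 6.2 and protocol 7.3.3, and changes results only if a roll-over gap exceeds 140 days.

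The cost is SAP wording and a few more tables. AE onset and dosing dates are already collected, so no new data are needed. The downside is small counts for rare events.

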10.2.1.1 Adverse Event Overview

The number and percentage of subjects experiencing TEAEs will be summarized for the following AE categories.

Any treatment-emergent adverse event.

Any treatment-emergent adverse event that was assessed with a Reasonable Possibility of being related to study drug by the Investigator.

- Any treatment-emergent severe adverse event.
- Any treatment-emergent serious adverse event.
- Any treatment-emergent adverse event leading to discontinuation of study drug.
- Any treatment-emergent adverse event leading to death.
- Any treatment-emergent adverse event of safety interest.

Any event with an unknown severity will be considered severe and any AE with an unknown relationship will be considered drug related.

10.2.1.2 Adverse Events by System Organ Class and Preferred Term

The number and percentage of subjects experiencing TEAEs will be tabulated using primary Medical Dictionary for Regulatory Activities (MedDRA) system organ classes (SOCs) and preferred terms (PTs) for each treatment group according to Version 18.0 or higher of the MedDRA coding dictionary. The SOCs will be presented in alphabetical order, and the PTs will be presented in alphabetical order within each SOC.

A subject who reports more than 1 AE in different SOCs will be counted only once in the overall total. A subject who reports 2 or more different PTs, which are in the same SOC, will be counted only once in the SOC total. Subjects reporting more than 1 AE for a given PT will be counted only once for that term (most severe incident for the severity tables and most related incident for the relationship tables).

10.2.1.3 Adverse Events by Maximum Severity

The severity grading of AEs follows Rheumatology Common Toxicity Criteria (RCTC).

- Grade 1 - mild
- Grade 2 - moderate
- Grade 3 - severe
- Grade 4 - life threatening

TEAEs will be summarized and tabulated by maximum severity in three categories: mild (Grade 1), moderate (Grade 2) and severe (Grade 3 or above) for data presentation. If a subject has an AE with an unknown severity, then the subject will be counted in the severity category of unknown, even if the subject has another occurrence of the same event with a severity present. The only exception is if the subject has another occurrence of the same AE with the most extreme severity – severe. In this case, the subject will be counted under the severe category.

AEs with Grade 3 or higher will be described in detail.

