10.2.1.4 Adverse Events by "Reasonably Possibly Related" Relationship

TEAEs will also be summarized by MedDRA SOC and MedDRA PT, assessed with a Reasonable Possibility of being related to study drug by the Investigator. If a subject has an AE with an unknown relationship, then the subject will be counted in as 'related.'

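### SAP 10.2.1.1 counts an ungraded AE as severe but 10.2.1.3 counts the subject as unknown, so two severe-TEAE counts can differ if a grade is missing (minor)

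*SAP*

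**What the plan says.** SAP 10.2.1.1 defines the adverse event overview. One of its rows is "Any treatment-emergent severe adverse event", and its closing rule is "Any event with an unknown severity will be considered severe".

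SAP 10.2.1.3 defines the maximum-severity table. TEAEs are to be "tabulated by maximum severity in three categories: mild (Grade 1), moderate (Grade 2) and severe (Grade 3 or above"). The section then brings in a category outside those three: a subject with an ungraded AE is "counted in the severity category of unknown, even if the subject has another occurrence of the same event with a severity present". It gives one way out: "The only exception is if the subject has another occurrence of the same AE with the most extreme severity", in which case the subject is placed under severe.

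Both outputs count subjects, because SAP 10.2.1 bases all AE analyses on patients rather than events.

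Unknown relationship is treated the same way throughout. SAP 10.2.1.1 takes it as drug related, and SAP 10.2.1.4 agrees: "If a subject has an AE with an unknown relationship, then the subject will be counted in as" related.

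**The concern.** Two outputs of one report will each carry a number of subjects with a severe TEAE, and a reader will expect the numbers to match. As written, they match only when no affected grade is missing. The SAP does not say that the rules are meant to differ between tables, and the section that uses an unknown category leaves it out of the categories it announces. A programmer following the text must decide whether the table has three columns or four.

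What is at stake is the consistency of a safety summary in a trial whose primary objective is long-term safety. No test, stopping rule or dose decision depends on the count.

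**Working it through.** No sample size, power or error-rate figure is involved, so the check is to apply both rules to the same subjects.

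**Inputs**
- Overview rule: ungraded is severe (SAP 10.2.1.1).
- Maximum-severity rule: ungraded outranks mild and moderate; severe outranks ungraded when it is on the same AE (SAP 10.2.1.3).
- Planned patients: about 60 (SAP 4.2), used only to scale an illustration.
- Number of ungraded TEAEs: not given in the documents, so taken as a range.

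**Step 1. One preferred term, one or two occurrences**

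| Grades present | Overview | Maximum-severity table | Severe counts agree? |
|---|---|---|---|
| Mild and/or moderate only | not severe | mild or moderate | yes |
| Severe, alone or with a graded occurrence | severe | severe | yes |
| Ungraded only (once or twice) | severe | unknown | no |
| Ungraded and mild | severe | unknown | no |
| Ungraded and moderate | severe | unknown | no |
| Ungraded and severe | severe | severe | yes |

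Every disagreement involves a missing grade, and in each one the overview is the higher count.

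**Step 2. The any-TEAE row**

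The overview counts as severe every subject with at least one TEAE that is Grade 3 or above or ungraded. In the 10.2.1.3 table each of those subjects falls under severe or under unknown, and no other subject does. Hence

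overview severe = table severe + table unknown,

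and the gap (overview severe − table severe) equals the table's unknown count.

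One case is open. Take a subject who is ungraded on one preferred term and Grade 3 on another. The exception speaks of the same AE, so in the any-TEAE row this subject is unknown on a literal reading and severe if the exception is applied per subject. The sum above holds either way; only the size of the gap changes:
- smallest gap: subjects with an ungraded TEAE and no TEAE of Grade 3 or above;
- largest gap: subjects with an ungraded TEAE and no severe occurrence of that same AE.

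**Step 3. Scale**

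Assume all 60 planned patients are treated, and let u be the number of subjects in the gap. The difference in the All Risankizumab column is 100 × u / 60 percentage points:
- u = 0: 0.0
- u = 1: 1.7
- u = 2: 3.3
- u = 3: 5.0

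The values of u are illustrative; nothing in the documents supports one over another. The sizes of the IV and SC columns are not given. Neither can exceed the All Risankizumab column, so one subject weighs at least as much there.

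**The case against.** The best defence is that the rules are specific to their tables. The overview is a short summary with no unknown row, so it counts conservatively; the severity table shows unknowns separately. Because overview severe equals severe plus unknown, a reader who sees the unknown column can reconcile the outputs. That is largely right, and it is why the issue is small. It does not remove the mismatch: the SAP does not state the relation, and the announced three-category layout has no column in which to see it.

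A reader might infer more from these sections than they support.

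- **A three-way conflict with SAP 10.2.1.2.** That section counts a subject once per preferred term by the "most severe incident for the severity tables and most related incident for the relationship tables", and one might say that it leaves the rank of unknown open, so that ungraded plus mild could count as mild. SAP 10.2.1.3 supplies the rank for the severity table: above mild and moderate, below severe. The conflict is between two rules only.
- **Doubt over which events are narrated.** "AEs with Grade 3 or higher will be described in detail" is clear. An ungraded event has no Grade 3, and the overview's counting convention does not give it one.
- **A likelihood of disagreement.** The share of rows that disagree in the pattern table is not a frequency. The list is unweighted and stops at two occurrences, and the disagreements arise only if a grade is missing. Protocol 5.2.2.1 requires RCTC grading of AE intensity.
- **Damage to the main safety results.** Protocol 7.3.3 puts the primary focus on drug-related AEs and serious infection. Neither count depends on how unknown severity is handled.

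One further point bears on the choice of remedy. SAP 9.1.2 rules out imputation of missing values outside efficacy, and protocol 7.4 plans none. Counting unknown as severe resembles imputation, and extending it would remove the separate unknown category. The point has limited force: 10.2.1.1 already uses the rule, and 9.1.2 itself imputes partial AE dates.

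**Conclusion.** The inconsistency is real and minor. Followed as written, SAP 10.2.1.1 and 10.2.1.3 give different numbers of subjects with a severe TEAE whenever a subject has an ungraded TEAE that the severity table places under unknown. The overview number is never the lower one, and the difference equals the unknown count in the any-TEAE row. The size cannot be derived from the documents: it is zero if every AE is graded, and 1.7 percentage points per affected subject if all 60 planned patients are treated. The analysis is descriptive and no decision rule uses the count. The point deserves a wording correction because that costs almost nothing and safety is the primary objective, not because any conclusion is at risk.

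**What to change.** Make the treatment of unknown severity consistent across the two sections, in one of two ways.

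1. Apply the 10.2.1.1 rule in 10.2.1.3, so that unknown counts as severe in both. This fits the three announced categories and parallels the handling of unknown relationship. Add a footnote with the number of ungraded AEs so that missing grades stay visible. The small cost is the loss of a separate unknown category.
2. Keep unknown, list it as a fourth category in 10.2.1.3, and footnote that the overview's severe count is severe plus unknown. This changes the current text least.

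Both are SAP wording edits that use severity data already collected.

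A separate, optional clarification: in SAP 12.7 the search criterion for serious infections names only the infections system organ class. Adding the words *serious TEAEs in* before it would make the criterion match its label. The label already shows the intent, and SAP 10.2.2 and 10.2.3 tabulate and list serious TEAEs, so this is not part of the finding.
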